## 2 List of Abbreviations

- SAP: Statistical analysis plan
- BALI: Balloon lithoplasty
- PCI: Percutaneous coronary intervention
- OCT: Optical Coherence Tomography
- MLA: minimal lumen area
- IVL: intravascular lithoplasty
- MSA: minimal stent area

## 3 Introduction

This document is the Statistical Analysis Plan (SAP) for a randomized (1:1), superiority, clinical trial comparing the use of balloon intravascular lithoplasty (IVL) to the current conventional techniques of routine lesion preparation before implantation of newest-generation drug-eluting stents in severely calcified coronary lesions. The protocol for this trial been registered at ClinicalTrials.gov. Version 5.3 of the protocol was used to make this SAP.

### 3.1 Objectives, Endpoints, and Estimands

#### 3.1.1 Primary

The primary objective is to show that the use of balloon lithoplasty for routine lesion preparation is superior to the current conventional techniques used for routine lesion preparation before implantation of newest-generation drug-eluting stents in severely calcified coronary lesions. The primary outcome is a composite of measures indicating procedural failure and 1-year target vessel failure. Specifically, the two intervention being compared are:

- Routine lesion preparation with balloon intravascular lithoplasty (IVL) with or without the use of rotational atherectomy at the operators discretion, and
- Routine lesion preparation with conventional techniques using conventional balloons, modified balloons, or high-pressure balloons with or without the use of rotational atherectomy at the operators discretion

prior to implantation of newest-generation drug-eluting stents in severely calcified coronary lesions. After the procedure, patients are followed for one year to determine the primary composite endpoint. The primary composite endpoint is determined by the following:

- Failed or no stent delivery determined by the angiographic core laboratory.

Failed or no stent delivery is defined as failure to deliver and deploy 1 or more coronary stents to cover the intended length of the intended target lesion.

- OCT-assessed residual area stenosis  $\geq 20\%$ .

Residual area stenosis is defined as  $1 - [\text{in-stent minimal lumen area (MLA)} / \text{reference lumen area}]$ . Residual area stenosis will be determined primarily by OCT, or, if necessary, by quantitative coronary angiography, as defined in the OCT and quantitative coronary angiography definitions section of the protocol. The use of angiography is a form of imputation and we will investigate the impact of this in Section 7.1.2.

- Target vessel failure within one year.

Defined as cardiac death, target vessel-related myocardial infarction, or clinically driven target vessel revascularization.

- Cardiac death is defined as death due to coronary heart disease, sudden cardiac death, heart failure including cardiogenic shock, and death related to the cardiac procedure within 28 days from the procedure. If death is not clearly attributable to other non-cardiac causes, it is adjudicated as cardiac.
- Target vessel myocardial infarction is defined as myocardial infarction according to the 4th Universal definition of Myocardial Infarction or peri-procedural myocardial infarction within 48 hours. Peri-procedural myocardial infarction is defined according to ARC-2 criteria: Troponin elevation of 35 times the 99th URL (or CK-MB elevation of  $>5$  times the 99th URL) and either: ST-segment changes, new pathological Q waves, angiographic evidence of a flow limiting complication (loss of patency of a side branch, persistent slow-flow or no-reflow, or embolization), imaging evidence of new loss of viable myocardium, or new wall motion abnormality within 48 hours after the PCI. In patients with elevated biomarkers prior to the procedure, the post-procedure troponin must rise by  $>20\%$  and still be  $>35$  times the 99th percentile URL. MIs will default to target vessel-related MIs unless there is other proof of definite attribution to a non-target vessel.
- Clinically-driven target vessel revascularization is defined as coronary artery bypass grafting or PCI of index vessel performed due to symptoms or signs of ischemia.

Accordingly, the primary estimand is described by the following attributes:

- Population: Adults with severely calcified coronary lesions with indication for PCI, the specific population is defined by the inclusion and exclusion criteria as given in Section 4.
- Endpoint: is a composite of procedural failure and within 1-year target vessel failure.
- Treatment: The interventions are conventional lesion preparation and preparation including balloon lithoplasty prior to implantation of newest-generation drug-eluting stents
- Intercurrent events:
  - Failure to obtain all information needed to evaluate the primary composite endpoint for reasons other than death from a cause not included in the primary endpoint, i.e. reason other than cardiac death. This will be addressed in the “Sensitivity Analyses for missingness” in Section 7.1.2.
- Population-level summary: Difference in 1-year risk of composite endpoint of procedural failure and within 1-year target vessel failure.

**Remark:** The justification for the "Intercurrent Events" is that we wish to report the difference in the risk of the primary endpoint comparing the two interventions in a world where people may die of other causes within the year, thus non-cardiac death is not an intercurrent event. The estimand of interest is made clear by the population of interest being among all patients and not just those that do not die from other causes.

We recognize that by ignoring non-cardiac death, we allow for the possibility that an intervention that kills people in some unexpected way would be considered superior by our primary estimand. Thus, as outlined in Section 7.1.1, we will never report the findings of the primary analysis without also reporting a comparison of the incidence of non-cardiac death between the intervention arms.

Correspondingly, the primary clinical question of interest is:

"What are the risks of the composite endpoint among patients randomized to receive IVL for lesion preparation before implantation of newest-generation drug-eluting stents in a severely calcified coronary lesion, and how does this risk compare to using the current conventional techniques of lesion preparation, regardless of actual use of balloon lithoplasty, additional interventions performed during initial PCI or additional treatments during the one-year after procedure, or other changes in status of patients not included in the endpoint of interest?"

### 3.1.2 Key Secondary Endpoints

#### Safety Endpoints

1. major adverse cardiac events and its components within one year:
  - 1a Cardiac death at or before one year after the index procedure
  - 1b Any myocardial infarction at or before one year after the index procedure
  - 1c Stroke at or before one year after the index procedure
2. In-hospital procedure events
  - 2a Periprocedural myocardial infarction
  - 2b Coronary dissection (flow-limiting or beyond intended by lesion preparation)
  - 2c Coronary perforation/rupture

#### Efficacy Endpoints

1. Components of the primary composite endpoint:
  - 3a Failed or no stent delivery
  - 3b Residual area stenosis  $\geq 20\%$  (OCT-assessed) after PCI
  - 3c Target vessel failure at 1 year
2. Components of target vessel failure at 1 year:
  - 4a Cardiac death
  - 4b Target vessel-related myocardial infarction
  - 4c Clinically driven target vessel revascularization.
3. OCT endpoints

- 5a Stent expansion at index procedure, MSA divided by the average reference area.
- 5b In-stent late lumen loss up to 1 year, which is the decrease in MLA area from the index procedure.

Correspondingly, the secondary objectives are to estimate the risks for each of the secondary outcomes if they are binary, and some comparison of those risks by arm, or to estimate the average values of continuous measures and some comparison of those average values by arm. The clinical questions of interest are:

**Safety:**

"What are the risks of any major adverse cardiac event overall and via the pathways of cardiac death, any myocardial infarction or stroke within one year among patients randomized to receive IVL for lesion preparation before implantation of newest-generation drug-eluting stents in a severely calcified coronary lesion, and how does this risk compare to using the current conventional techniques of lesion preparation, regardless of actual use of balloon lithoplasty, additional interventions performed during initial PCI or additional treatments during the one-year after procedure, or other changes in status of patients not included in the endpoint of interest?"

"What are the risks of any in-hospital procedure event overall and via the pathways of periprocedural myocardial infarction, coronary dissection being beyond intended by lesion preparation or coronary perforation/rupture among patients randomized to receive IVL for lesion preparation before implantation of newest-generation drug-eluting stents in severely calcified coronary lesion, and how does this risk compare to using the current conventional techniques of lesion preparation, regardless of actual use of balloon lithoplasty, additional intervention performed during initial PCI or additional treatments during the one-year after procedure, or other changes in status of patients not included in the endpoint of interest?"

**Efficacy:**

"What are the risks of failed or no stent delivery, OCT-assessed residual area stenosis  $\geq 20\%$  or target vessel failure within one year among patients randomized to receive IVL for lesion preparation before implantation of newest-generation drug-eluting stents in severely calcified coronary lesion, and how does this risk compare to using the current conventional techniques of lesion preparation, regardless of actual use of balloon lithoplasty, additional intervention performed during initial PCI or additional treatments during the one-year after procedure, or other changes in status of patients not included in the endpoint of interest?"

"What are the risks of target vessel failure within one year via the pathways of cardiac death that is possibly related to target vessel failure, target vessel-related myocardial infarction, or clinically driven target vessel revascularization within a year of index procedure among patients randomized to receive IVL for lesion preparation before implantation of newest-generation drug-eluting stents in severely calcified coronary lesion, and how does this risk compare to using the current conventional techniques of lesion preparation, regardless of actual use of balloon lithoplasty, additional intervention performed during initial PCI or additional treatments during the one-year after procedure, or other changes in status of patients not included in the endpoint of interest?"

"What is the average stent expansion among patients having IVL for lesion preparation at index procedure and how does this stent expansion compare to using the current conventional techniques

of lesion preparation, regardless of actual use of balloon lithoplasty?"

"What is the average in-stent late lumen loss among patients undergoing IVL for lesion preparation at index procedure and how does this in-stent late lumen loss compare to using the current conventional techniques of balloon lesion preparation, regardless of actual use of balloon lithoplasty, additional intervention performed during initial PCI or additional treatments during the one-year after procedure, or other changes in status of patients not included in the endpoint of interest?"

### 3.1.3 Exploratory

There are several exploratory endpoints:

- Procedural endpoints
  - Complications (many)
  - Procedure details (durations/doses etc)
  - Procedure cost
- OCT endpoints at index procedure
  - Stent malapposition
  - Calcium disruption
- OCT endpoints at 1 year
  - In-segment late lumen loss
  - In-segment re-stenosis
  - Stent malapposition
- Symptom status at 1 year

Here, we do not specify a hypothesis, as we will also not report p-values from any exploratory analysis.

## 4 Population

Inclusion criteria

- Age  $\geq 18$  years and  $< 90$  years
- Stable coronary heart disease or non-ST elevation acute coronary syndrome
- PCI planned in a severely calcified, non-occluded, de-novo lesion in a native vessel.
- Functional evidence of ischemia (non-invasive stress test or fractional flow reserve) in the target vessel territory or stenosis  $\geq 90\%$  by visual estimate
- Target vessel reference diameter visually estimated at 2.5-4 mm on angiography with ability to pass a 0.014" guidewire across lesion

- Ability to tolerate dual antiplatelet therapy
- Informed consent

Exclusion criteria

- Study lesion is unprotected left main
- Chronic total occlusion of study lesion
- Severely calcified bifurcated lesion with expected need to use two-stent technique
- Coronary artery dissection of study lesion
- ST-segment elevation acute myocardial infarction within 72 hours
- Planned later revascularization in non-study lesions (other lesions in need of revascularization must be treated before treatment of the study lesion, either staged or during the study procedure)
- Planned cardiovascular interventions within 30 days after study intervention
- Clinical instability including decompensated heart disease
- Life expectancy of less than 1 year
- Active peptic ulcer or upper gastrointestinal bleeding within 6 months
- Ongoing systemic infection
- Pregnant or nursing
- Left ventricular ejection fraction < 35%
- Renal function with eGFR < 30 mL/min

#### 4.1 Study Design

This is a two-arm, randomized (1:1), parallel, multinational open-label but assessor-blinded superiority clinical trial. The assessment of the primary outcome is blinded. Patients are booked for clinical follow-up 12 months after the procedure. At the clinical follow-up clinical events relevant to the primary endpoint are recorded prior to coronary angiography. OCT is performed again at this time (prior to any additional intervention, if conducted), and the results are available to the operator. As the clinical follow-up occurs prior to the coronary angiography, events triggered by coronary angiography are not part of the primary endpoint at one year.

### 5 Multiplicity Adjustment

No multiple testing correction will be used, as formal hypothesis testing will be performed only for the primary endpoint/estimand described in Section 3.1.1, for the null hypothesis defined in Section 7.1.1.

Reporting for other endpoints/estimands will either be limited to point estimates of effects with 95% (two-sided) confidence intervals, or p-values will be noted explicitly as secondary. The widths of the intervals will not be adjusted for multiplicity; therefore, it will not be possible to use them in place of formal hypothesis testing. This is in line with current recommendations [8].

## 6 Analysis Sets

- The “**Main analysis set A**” consists of all randomized participants who have a complete measure of the primary composite endpoint. This will exclude three groups of patients: patients who withdraw consent prior to 1 year and explicitly do not wish to participate in the 1-year clinical follow-up data collection, patients that are deemed to be lost to follow-up by the Clinical Endpoint Adjudication Board (see section 4.3 of protocol version 5.3), and patients who lack baseline OCT or Quantitative coronary angiography.
- The “**Sensitivity analysis set or Main analysis B**” consists of all randomized participants.
- **Secondary Safety endpoint analysis set 1, 1a, 1b, 1c:** consists of all randomized participants who have a measure of in-hospital and 1 year major adverse cardiac events for set 1, all randomized participants who have a measure of Cardiac death at or before one year after the index procedure, 1a, all randomized participants who have a measure of any myocardial infarction at or before one year after the index procedure, 1b, and all randomized participants who have a measure of stroke at or before one year after the index procedure, 1c.
- **Secondary Safety endpoint analysis set 2, 2a, 2b, 2c:** consists of all randomized participants who have a measure of in-hospital procedure events overall, 2, of periprocedural myocardial infarction, 2a, coronary dissection (beyond intended by lesion preparation), 2b, and coronary perforation/rupture, 2c. As it is very likely that all randomized participants will have measures of these events or be followed to know that the event did not occur, all of these groups may be the same as “Sensitivity analysis set or Main analysis B”

## 7 Statistical Analyses

### 7.1 Primary Endpoint Analysis

#### 7.1.1 Main Analytical Approach

For this analysis, we will use the “Main analysis set A” detailed in Section 6. We will estimate the primary estimand, that is, the risk ratio  $\pi_1/\pi_0$ , as the empirical (i.e. observed) proportion of participants with the composite endpoint within 12 months after index PCI. An appropriate two-sided 95% confidence interval and matching p-value for the null hypothesis:  $H_0 : \pi_1/\pi_0 = 1$  will be computed.

We will use the function `uncondExact2x2` of the R package `exact2x2`; see [2] for the mathematical details and Appendix 9.2 for the specific R code that we will use. If the p-value is  $\leq 0.05$  and the risk ratio is  $< 1$  for the composite primary endpoint then we will consider this evidence of the superiority of balloon lithoplasty preparation of lesions in comparison to current conventional techniques to reduce the risk of the composite endpoint. If the p-value is  $\leq 0.05$  and the risk ratio is  $> 1$ , we will consider this evidence of harm of balloon lithoplasty preparation of lesions in comparison to current conventional techniques, i.e. it increases the risk of the composite endpoint.

Using dataset “Main analysis set B” detailed in Section 6, we will, in addition, estimate the difference in risk  $\pi_1 - \pi_0$  of all mortality that is not cardiac death within at least 12 months; the competing risk of the composite endpoint. An appropriate exact two-sided 95% confidence interval for the parameter  $\pi_1 - \pi_0$  will be computed. This will be reported regardless of the result of the above analysis. We will again use the function `uncondExact2x2` of the R package `exact2x2`; see

[2] for the mathematical details and Appendix 9.2 for the specific R code that we will use. The primary composite endpoint results will never be presented without the results for all other causes of mortality unless there are no other deaths in the full trial.

In addition, regardless of the results, we will report the estimates of the arm-specific risk of the composite endpoint and the risk of mortality that is not cardiac death within one year (i.e. the empirical proportions) together with exact binomial two-sided 95% confidence intervals (computed using the `binom.test()` function of R).

Note that the above statistical analyses will ignore that the randomization was stratified by site. This is usually not recommended, as this usually leads to a decrease in power as stratification variables are precision variables [3, 7]. However, our context is very specific, as we expect for there to be a low number of composite endpoint events, at least in the IVL arm. This has two important consequences. First, the loss of power is expected to be negligible. Second, ensuring proper type-I error control using a “covariate-adjusted” alternative approach is difficult using standard software. Additionally, the impact of not adjusting will be investigated as part of the Sensitivity Analyses.

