### Safety endpoints

1. In-hospital and 1 year major adverse cardiac events and its components:
  - 1a Cardiac death at or before one year after the index procedure
  - 1b Any myocardial infarction at or before one year after the index procedure
  - 1c Stroke at or before one year after the index procedure
2. In-hospital procedure events
  - 2a Periprocedural myocardial infarction
  - 2b Coronary dissection (beyond intended by lesion preparation)
  - 2c Coronary perforation/rupture

For binary efficacy endpoints we will use the same exact testing as for the primary composite end point for binary outcomes and site adjusted linear regression for continuous outcomes. For all secondary efficacy analyses we will use the “Main analysis set A” detailed in Section 6, to make the results comparable and on the same set as the primary.

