## 8 Sample Size Determination and Power Calculation

In the protocol, it was stated that to reach 80% power to detect a true difference of 15%, with 25% in the standard of care group and 10% events in the IVL group for a two-sided test with alpha of 0.05, 194 patients total, 97 per arm, are needed when randomized 1:1. However, it was planned to enroll 200 patients to allow for a low level of loss to follow-up.

Instead, when using the intended exact method, we find that 194, 97 per arm, only provides 78% power for the hypothesized true difference in risks. Using the intended enrollment of 100 per arm, we reach the desired 80% power. These power calculations were carried out using the Power2x2 function, as outlined below.

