## 9 Supporting Documentation

### 9.1 R Code for Power calculations (Primary Estimand Analysis)

```
library(exact2x2)
Power2x2(n1,n2,.1,.25,0.05, pvalFunc=
  function(x1,n1,x2,n2){
    uncondExact2x2(x1,n1,x2,n2,
      parmtype="ratio", method="FisherAdj", midp=FALSE)$p.value
  }
)
```

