### 9.2 R Code for the Exact Unconditional Test (Primary Estimand Analysis)

```
library(exact2x2)
uncondExact2x2(x1=x1obs,                                # x1obs is the number of events in IVL group
               n1=n1obs,                                # n1obs is the number of patients in IVL group
               x2=x2obs,                                # x2obs is the number of events in SOC group
               n2=n2obs,                                # n2obs is the number of patients in SOC group
               parmtype="ratio",                         # estimand is risk ratio
               alternative="two.sided",                  # using Fisher's exact for ordering of the
               method="FisherAdj",                       # parameter space
               midp=FALSE,                               # midp False so that it is exact in all cases
               not just exact on average
               conf.level = 0.95,                         # 95% confidence level
               conf.int=TRUE)                            # indicating to compute a CI
```

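### The primary risk-ratio interval is built on a Fisher ordering fixed at equal risks, so it is valid but close to uninformative: lower limit 0 whenever IVL is clearly better, and upper limit about 0.97 at the design effect

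*SAP*

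**What the plan says.** Section 7.1.1 estimates the primary effect as the risk ratio of IVL to control and promises "An appropriate two-sided 95% confidence interval and matching p-value for the null hypothesis" that the ratio is 1. Superiority is declared if the p-value is at most 0.05 and the observed ratio is below 1.

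Section 9.2 obtains the p-value and the interval from one call to `uncondExact2x2`, with the ratio as parameter, `FisherAdj` as method, mid-p switched off and the interval requested. The comment on the method reads "using Fisher's exact for ordering of the" (it continues on the next line). Section 9.1 uses the same ordering for power.

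Section 9.3 uses the score ordering for the difference in non-cardiac mortality. The SAP gives no reason for ordering the primary analysis differently.

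The primary call is reused. In Section 7.3: "For binary efficacy endpoints we will use the same exact testing as for the primary composite end point". Section 7.4 says the same for binary exploratory endpoints.

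**The concern.** A Fisher ordering ranks tables by their evidence against equal risks. For a test of ratio 1 that is sensible. A confidence limit asks a different question: is the observed table compatible with a ratio of 0.1, or of 0.9? An ordering that cannot re-centre on the tested value answers poorly once the tail probability is maximised over the unknown control risk.

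At stake is the precision reported with the trial's only confirmatory result. An interval from 0 to almost 1 cannot separate a very large benefit from a slight one, and it includes a ratio of 0 even when the IVL arm has events. The consequence may be greater for secondary and exploratory endpoints. Section 5 reports endpoints other than the primary as estimates with 95% intervals, or with p-values marked as secondary, and Section 3.1.3 rules out p-values for exploratory endpoints. The interval may therefore be the only inferential result shown.

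**Working it through.** **Inputs (SAP Section 8).** Event risks "with 25% in the standard of care group and 10% events in the IVL group", a ratio of 0.10/0.25 = 0.40; "for a two-sided test with alpha of 0.05"; 97 per arm from the protocol and 100 per arm as intended enrolment. Methods are from Sections 9.1 to 9.3. The R package was not available, so the test was reimplemented by enumerating all tables.

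**1. Reproduce the SAP's figures.**
- Chi-squared size, unpooled: n = (1.960 + 0.842)² × (0.10×0.90 + 0.25×0.75) / 0.15² = 7.849 × 0.2775 / 0.0225 = 96.8, so 97 per arm, as stated.
- Exact power: sum of Bin(x1; n, 0.10) × Bin(x2; n, 0.25) over tables with p ≤ 0.05. Here p is twice the smaller tail probability, each tail maximised over the common risk.
- Fisher mid-p ordering: 78.2% at 97 per arm and 80.3% at 100. Plain Fisher p ordering: 77.5% and 79.2%. The SAP states "194, 97 per arm, only provides 78% power", and 80% at 100 per arm. The mid-p ordering matches both figures.

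**2. Lower limit, 10 v 25 of 100.** A ratio r is excluded from below only if the largest probability, over control risk p, of a table no more favourable to IVL than the observed one is at most 0.025. The observed table has a one-sided Fisher mid-p of 0.0028. The table with no events in either arm has 0.5, so it always counts as less favourable. Its probability is (1 − p)^100 × (1 − rp)^100, which tends to 1 as p tends to 0. With r = 0.1 and p = 0.0001 it is 0.9999^100 × 0.99999^100 = 0.990 × 0.999 = 0.989. No small ratio can be excluded, so the lower limit is 0.

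Removing the no-event table does not help. At r = 0.001 the maximum is still 0.948, at p = 0.034. Tables with 0 IVL events and 1 to 7 control events make up almost all of it, because 0 v 7 has mid-p 0.0035, above 0.0028.

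**3. Upper limit, 10 v 25.** A ratio is excluded from above when the largest probability of a table at least as favourable to IVL falls to 0.025 or below.

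| Ratio tested | Largest tail probability | Control risk where reached |
|---|---|---|
| 0.80 | 0.9997 | 1.00 |
| 0.90 | 0.79 | 1.00 |
| 0.95 | 0.13 | 1.00 |
| 0.9675 | 0.030 | 0.98 |
| 0.97 | 0.024 | 0.98 |
| 1.00 | 0.0028 | 0.50 |

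The limit is about 0.97. It is set by control risks near 100%, where even a ratio just below 1 produces small Fisher p-values. The last row gives the two-sided p-value, 2 × 0.0028 = about 0.006.

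**4. Comparison with the score ordering.** Same inversion, but with the score statistic for the ratio recomputed at each tested value (100 per arm).

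| IVL v control events | Ratio | Fisher ordering | Score ordering |
|---|---|---|---|
| 10 v 25 | 0.40 | 0 to 0.97 | 0.18 to 0.79 |
| 8 v 22 | 0.36 | 0 to 0.97 | 0.13 to 0.78 |
| 5 v 25 | 0.20 | 0 to 0.92 | 0.06 to 0.48 |
| 2 v 30 | 0.07 | 0 to 0.84 | 0.01 to 0.23 |

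Check on the first row by log-Wald: SE = √(1/10 − 1/100 + 1/25 − 1/100) = √0.12 = 0.346; exp(ln 0.40 ± 1.96 × 0.346) = 0.20 to 0.79.

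**5. Power after the change.** With score ordering, power is 78.2% at 97 per arm and 80.4% at 100.

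**The case against.** The strongest reply is that nothing confirmatory depends on this interval. The decision rule uses the p-value and the direction of the observed ratio. Type I error, power and the point estimate all stand, and the interval has at least nominal coverage and agrees with its p-value. That is correct: the interval is inefficient, not invalid.

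A reader might infer that the interval says nothing about effect size, or that its upper limit merely repeats that p is at most 0.05. That goes too far. The upper limit falls to about 0.92 at 5 v 25 and 0.84 at 2 v 30, so a weak one-sided bound remains. It is the lower limit that is empty.

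Other precision measures are planned: exact binomial intervals for each arm's risk (Section 7.1.1) and standardised risk ratios from logistic regression (Section 7.1.2). Neither is an interval for the primary ratio from the primary analysis.

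Finally, the package itself was not run, and the SAP code does not say how the control risk is restricted in the maximisation. This matters for the upper limit. Restricting the control risk to a 99.9% to 99.9999% confidence range, with the usual penalty, gave about 0.83 to 0.86 at 10 v 25. The lower limit stayed at the bottom of the grid searched (0.01), so the main fault does not depend on this choice. It also appears with either Fisher p or mid-p ordering.

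**Conclusion.** The point holds as a fault in the reported interval, not in the test. At 10 v 25 of 100 the planned code would give about 0 to 0.97, where an equally exact alternative gives about 0.18 to 0.79. In the clearly favourable results examined the lower limit is 0, however strong the result.

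The figure of 0.97 assumes that the control risk is maximised over its whole range. The zero does not need that assumption. All figures assume that the reimplementation matches the package, which is supported by its reproducing the SAP's 78% and 80% but remains to be confirmed. The documents give no ground for doubting the primary p-value, the superiority rule or the stated power on this account.

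**What to change.** 1. Before unblinding, run the Section 9.2 code on 10/100 v 25/100 and check whether the lower limit is 0.
2. If confirmed, replace `FisherAdj` with `score` in Sections 9.1 and 9.2, keeping the ratio as parameter, the two-sided alternative and mid-p off. Take the p-value and interval from this one call, and apply it wherever Sections 7.3 and 7.4 refer back to the primary exact method. Rerun the power call; the expected values are 78.2% at 97 per arm and about 80.4% at 100.
3. If the sponsor prefers to keep the Fisher-ordered p-value, prespecify the score-ordered exact interval for the ratio alongside it, and state that the two may disagree in rare borderline tables.

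The cost of option 2 is one argument in two code blocks. Exactness is kept, but a few borderline tables get slightly different p-values, which is why the choice must be made before unblinding. Option 3 leaves the test untouched but gives up the guaranteed match between p-value and interval that Section 7.1.1 promises.
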